8.3 Exploratory Endpoints/Correlative Studies

Subjects who receive at least 2 cycles of belimumab are evaluable for explorative endpoints/correlative studies.

Age- and disease-matched controls with matched conditioning regimens and donor source/mismatch status will be obtained from the Bone Marrow Transplant Tissue Bank at Siteman Cancer Center at Washington University in St. Louis. These patients have had peripheral blood samples stored at time of transplant, 30 days post-transplant, 100 days post-transplant, 180 days post-transplant, and 360 days post-transplant. Immune competence and B cell phenotype subset panels will be performed on these samples. Additionally, BAFF levels will be measured and correlated with development of GvHD similarly to study cohort. The clinical outcomes including survival, recurrence rate, engraftment, incidence of acute and chronic GvHD, and medications list are readily available in institutional computerized database.

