13 STATISTICAL ANALYSIS

This trial is designed to allow preliminary assessments of safety/tolerability and efficacy of belimumab in the post-allogeneic stem cell transplant setting. No pre-specified hypothesis testing will be performed. All analyses of demographics, biological activity, and safety will be descriptive. A 90% exact binomial confidence interval will be constructed for preliminary efficacy information. Data obtained from correlative studies will be used to identify parameters associated with efficacy from belimumab treatment that will guide design of subsequent larger clinical trials. Age-, disease-, and donor-matched subjects will be used as an institutional control. These control subjects will be identified within the Bone Marrow Transplant and Lymphoma Tissue Bank (HRPO# 201103349). Presently, there are roughly 100 subjects with banked specimens and associated clinical outcomes data that will serve as the comparator in this study in assessing preliminary efficacy. The data from this study will be used for sample size calculation estimates of an expansion cohort in a subsequent phase II study. A total of N=10 patients will be enrolled for this study. Though the sample size was not determined based on statistical power, this would provide us reasonable precision on both safety and feasibility. Based on intensive simulation studies regarding the sample size for pilot and translational studies, Piantadosi (2005) recommends that a sample size of 10 to 20 patients be adequate to provide preliminary information. For safety assessment, for example, there would be 90% chance of observing at least 1 serious adverse event if the true rate is at least 20%. Conversely, there would be less than 10% chance that we would observe 2 or more serious adverse events if the true rate is less than 5%.

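### The efficacy controls come from a specimen bank described as sampled to Day 360; to the extent they are chosen for that sample, their 12-month survival is inflated

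*Combined protocol and SAP*

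**What the plan says.** Section 13 describes its control pool as "roughly 100 subjects with banked specimens and associated clinical outcomes data that will serve as the comparator in this study in assessing preliminary efficacy". It matches on age, disease and donor.

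Section 8.3 draws controls from the same bank, adds conditioning regimen to the matching, and says of them: "These patients have had peripheral blood samples stored at time of transplant, 30 days post-transplant, 100 days post-transplant, 180 days post-transplant". The list of sampling times then closes with a fifth: "and 360 days post-transplant". The immune and B-cell panels are to be run on those samples. It adds: "The clinical outcomes including survival, recurrence rate, engraftment, incidence of acute and chronic GvHD, and medications list are readily available" from the institutional database.

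On the treated side, Section 5 starts belimumab between Day +30 and Day +80. Section 8.2 makes subjects evaluable for secondary endpoints only after two or more cycles. It reports chronic GvHD, survival and relapse at 6, 12 and 24 months after transplant, yet counts survival and relapse from the start of belimumab.

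For controls, no section gives an index date, an entry state at that date, or a rule for patients who lack later samples.

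**The concern.** A patient who died before Day 360, or stopped attending, cannot have a Day-360 sample. If having that sample decides who becomes a control, membership of the comparator depends on an event after time zero. Matching on age, disease, conditioning and donor cannot remove that kind of selection.

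The 12-month assessment falls almost on the Day-360 draw, so survival is the endpoint most exposed. Control outcomes are also already on file when the controls are picked, and nothing masks them.

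The comparison is descriptive, so no error rate is at stake. However, Section 13 says that data from this study will feed the sample-size estimates for a later phase II cohort. A distorted control rate would pass into that calculation.

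**Working it through.** **The plan's own figures.** Section 13 gives two probabilities for n = 10, both about serious adverse events.
- At a true rate of 20%, P(at least 1) = 1 − 0.80^10 = 0.893 (stated: 90%).
- At a true rate of 5%, P(2 or more) = 1 − 0.95^10 − 10 × 0.05 × 0.95^9 = 0.086 (stated: below 10%).

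Both reproduce. Neither bears on the comparator, for which the plan gives no figure.

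**Inputs from the documents.** Control sampling at transplant and Days 30, 100, 180 and 360 (Section 8.3); belimumab start at Day 30 to 80 (Section 5); Cycle 2 two weeks later, ± 3 days (Section 5.2); chronic GvHD in 40–60% of long-term survivors (Section 1.1).

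**Assumed inputs, because the documents give none.**
- S, true 12-month survival: 0.60 to 0.90.
- f, share of controls chosen because a Day-360 sample exists: 0 to 1. The other controls are taken to be representative.
- d, share dying within the year: 0.10 to 0.40.
- q, chronic GvHD rate before death among those who die: 0.10 to 0.70.

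**Step 1: survival.** Apparent control survival = f + (1 − f)S, so the inflation is f(1 − S). Day 360 is treated as 12 months.

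| S | f = 0 | f = 0.25 | f = 0.5 | f = 1 |
|---|---|---|---|---|
| 0.90 | 0 | 2.5 points | 5 points | 10 points |
| 0.80 | 0 | 5 points | 10 points | 20 points |
| 0.70 | 0 | 7.5 points | 15 points | 30 points |
| 0.60 | 0 | 10 points | 20 points | 40 points |

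The sign is the same in every cell with f above zero: controls look better than they should.

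**Step 2: relapse.** Patients who relapse and die before Day 360 drop out of a set chosen this way, so control relapse is probably understated. The documents give no rates from which to size it.

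**Step 3: chronic GvHD.** With g the rate in survivors, the all-patient rate is (1 − d)g + dq. The survivor-only rate therefore differs from it by d(g − q). Here g is set to the protocol's 40–60%, although that figure carries no time point.
- g = 0.60, d = 0.40, q = 0.10: 0.40 × 0.50 = +20 points.
- g = 0.40, d = 0.40, q = 0.70: 0.40 × (−0.30) = −12 points.
- q = g: zero.

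The sign turns on whether those who die early had chronic GvHD less or more often than survivors. The documents do not say.

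**Step 4: selection in the belimumab group.** The second cycle falls between Day 30 + 14 − 3 = 41 and Day 80 + 14 + 3 = 97. Under a constant hazard, survival to Day 365 given alive at day t is S^((365 − t)/365).
- S = 0.90 becomes 0.911 to 0.926, a gain of about 1 to 3 points.
- S = 0.80 becomes 0.820 to 0.849, a gain of 2 to 5 points.
- S = 0.60 becomes 0.635 to 0.687, a gain of about 4 to 9 points.

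This applies if controls are counted from transplant. Most of it comes from the entry window. The 2-cycle rule alone adds 0.908 to 0.911 (Day 30 to 41) up to 0.671 to 0.687 (Day 80 to 97), or about 0.3 to 1.6 points.

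**Step 5: precision.** The planned 90% exact interval for ten subjects runs from 22.2% to 77.8% at 5/10 and from 49.3% to 96.3% at 8/10.

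**The case against.** The strongest reply is that no section makes a Day-360 sample a selection criterion. The stated criteria are matching variables. Section 13, which names the efficacy comparator, asks for banked specimens with no time point. A patient who died on Day 200 could have four banked samples and still qualify. The Section 8.3 sentence sits under correlative studies and can be read as a collection schedule, and survival is listed among the control outcomes. All of this stands, so f is unknown and may be zero. It does not remove the problem: the panels are run on those samples, and nothing prevents a preference for patients with complete sets. Listing survival does not show that early deaths are included either, since survival is also assessed at 24 months.

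A second reply is that the treated group is selected too. That is correct. The two effects oppose each other, but neither is controlled and they need not cancel.

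A third reply is scale: "A total of N=10 patients will be enrolled for this study", the primary endpoint is safety, and "No pre-specified hypothesis testing will be performed". With intervals as wide as in step 5, a shift of a few points would not be visible in the belimumab estimate. This limits the importance of the point. It does not justify leaving the control definition open when Section 13 uses that group to assess efficacy and the study's data to plan phase II.

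**Conclusion.** The point holds in a conditional form. Read literally, Section 8.3 restricts controls to patients who survived and attended to Day 360. Read as a schedule, it leaves that restriction possible. The survival bias is f(1 − S): zero if no control is chosen for a Day-360 sample, and 10 to 40 points against belimumab if all are, for an assumed true survival of 90% to 60%. The opposing selection in the belimumab group is about 1 to 9 points on the same survival range, under a constant hazard and with controls counted from transplant.

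Two stronger readings are tempting, and the documents support neither. A reader might infer that the controls are one-year survivors by construction and that every 12-month comparison is therefore biased. That treats f = 1 as a fact, which no section states. A reader might also infer that control chronic GvHD is overstated, so that belimumab looks better on its target outcome. That needs death and chronic GvHD to be independent, or chronic GvHD to be rarer before early death. Section 1.1 calls chronic GvHD the most common cause of late non-relapse mortality, which argues against independence, and step 3 shows that either sign is possible.

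The change is worth making but is not critical to a safety pilot.

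**What to change.** In Sections 8.3 and 13:

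1. Define the clinical comparator as all matched patients in the bank or institutional database who, at a stated landmark day matched to the belimumab start (Day 30 to 80), are alive, in complete remission with full donor engraftment, and free of chronic GvHD. Include them whether or not later samples exist, and start follow-up at that landmark in both groups. Section 5.2 also gives Day +30 to +60 for Cycle 1, so the start window must be reconciled before the landmark is set.
2. Analyse all treated belimumab subjects in this comparison, or keep the 2-cycle rule and apply a matching later landmark to controls.
3. Use sample availability only to define the set for BAFF and flow cytometry. Label that set as conditional on being sampled, and report how many controls lack each sample.
4. Select controls from baseline fields and lock the list before outcomes are linked.

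The cost is revised wording and some database abstraction for patients without complete sample sets; no new patients or procedures are needed. The downside is that the clinical and specimen control sets will no longer be identical.

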9 CORRELATIVE STUDIES

All subjects will have blood drawn for correlative studies. Serum will be removed from a serum separator tube (SST) containing 10 mL patient blood, and peripheral mononuclear cells (PBMC) will be isolated from a 10 mL CPT tube at baseline and first follow-up post-belimumab (+24 wk), then every three months thereafter to assess BAFF levels and immune cell reconstitution. An additional serum sample will be collected prior to cycle 3 (+4 wk) to assess efficacy of belimumab in suppressing BAFF levels. BAFF levels will be quantitated by ELISA and immune cell reconstitution will be quantitated by whole blood flow cytometry.

Once there is evidence of B cell reconstitution (anticipate between 18-24 months post-transplant), serum (1 x 10 mL SST) and PBMC (5 x 10 mL CPT tubes) will be collected for isolation of the

mononuclear cell layer, or buffy coat, by Ficoll-based density separation for additional B cell phenotyping by flow cytometry. Similar blood collections will be performed at 1 and 2 years post-C1D1. Additional optional correlative lab draws will continue to be collected for similar analysis yearly thereafter up to 5 years post-C1D1. All samples will be processed and stored in the Dunn Lab ([name]) or Tissue Procurement Center until time of analysis.

The following variables will be assessed:

- Immune competence panel to quantify the relative frequency and absolute number of T cells, B cells, and NK cells which will determine impact of belimumab on immune reconstitution following transplantation.
- BAFF levels at baseline and following treatment to assess the efficacy of belimumab in suppressing this target cytokine as well as to correlate development of chronic GvHD with circulating BAFF levels (i.e. degree of inhibition).
- A B cell phenotype panel will be performed to assess the effect of belimumab on reconstitution and homeostasis of B cell subsets after transplant.
- Immunoglobulin subset quantification will be performed to determine the effect of belimumab on the functional competency of B cells after transplant.

10 STUDY CALENDAR

10.1 Screening and Treatment Calendar

	Screening ¹	Baseline ²	C1	C2 +2wk	C3 +4wk	C4 +8wk	C5 +12wk	C6 +16wk	C7 +20wk
Informed consent	X								
H&P, ECOG PS	X		X	X	X	X	X	X	X
VS	X		X	X	X	X	X	X	X
CBC	X		X	X	X	X	X	X	X
CMP, LDH, phosphate, uric acid, magnesium	X		X	X	X	X	X	X	X
Pregnancy test ⁷	X		X ⁸	X	X	X	X	X	X
IgG and IgA		X							
Hepatitis serologies	X								
ECG (triplicate)	X		As clinically indicated						
Belimumab			X ⁵	X ⁵	X ⁵	X ⁶	X ⁶	X ⁶	X ⁶
Research blood		X ²			X ⁴				
Acute GvHD assessment		X			X	X	X	X	X
Chronic GvHD assessment					X	X	X	X	X
Immunosuppressive medication assessment	X	X	X	X	X	X	X	X	X
Medication reconciliation		Monthly							
AE assessment		X ----- X ⁹							

1. Screening assessments must take place between 30 and 80 days post-transplant
2. pre-treatment
3. Every 3 months starting at F/U #1 (+24wk)
4. Prior to treatment
5. Dosing window is +/- 3 days
6. Dosing window is +/- 1 week
7. Women of childbearing potential only
8. Pregnancy test need not be repeated on Cycle 1 if conducted within 7 days of Cycle 1 dose
9. AE assessment continues for 30 days post-EOT

10.2 Follow-Up Calendar

Follow-up visits start 4 weeks after the end of protocol treatment (6-month follow-up is 6 months post-C1D1 and 4 weeks post-C7D1).

	+6mo	+9mo	+12mo	+15mo	+18mo	+21mo	+24 mo	+3 yr	+4 yr	+5 yr
CBC	X									
CMP, LDH, phosphate, uric acid, magnesium	X									
Pregnancy test ¹	X									
Research blood ²	X	X	X	X	X	X	X	X ²	X ²	X ²
Acute GVHD assessment	X									
Chronic GVHD assessment	X	X	X	X	X	X	X			
Immunosuppressive medication assessment	X	X	X	X	X	X	X			
AE assessment	X									

1. Women of childbearing potential only

2. Once there is evidence of B cell reconstitution, additional blood will be drawn (refer to Section 9), and will continue on an optional basis at 3, 4, and 5 years post-C1D1

11 DATA AND SAFETY MONITORING

In compliance with the Washington University Institutional Data and Safety Monitoring Plan, the Principal Investigator will provide a Data and Safety Monitoring (DSM) report to the Washington University Quality Assurance and Safety Monitoring Committee (QASMC) semi-annually beginning six months after accrual has opened (if at least 1 patient has been enrolled) or one year after accrual has opened (if no patients have been enrolled at the six-month mark).

For phase I dose escalation studies, the Principal Investigator will review all patient data at least monthly (or before each dose-escalation if occurring sooner than monthly), and provide a semi-annual report to the Quality Assurance and Safety Monitoring Committee (QASMC). For phase II or dose expansion cohorts of a phase I study, the Principal Investigator will review all patient data at least every six months, and provide a semi-annual report to the QASMC. This report will include:

- HRPO protocol number, protocol title, Principal Investigator name, data coordinator name, regulatory coordinator name, and statistician
- Date of initial HRPO approval, date of most recent consent HRPO approval/revision, date of HRPO expiration, date of most recent QA audit, study status, and phase of study
- History of study including summary of substantive amendments; summary of accrual suspensions including start/stop dates and reason; and summary of protocol exceptions, error, or breach of confidentiality including start/stop dates and reason
- Study-wide target accrual and study-wide actual accrual
- Protocol activation date
- Average rate of accrual observed in year 1, year 2, and subsequent years
- Expected accrual end date and accrual by cohort
- Objectives of protocol with supporting data and list the number of participants who have met each objective
- Measures of efficacy (phase I studies only if efficacy is objective of the protocol)
- Early stopping rules with supporting data and list the number of participants who have met the early stopping rules
- Power analysis and/or interim analysis (if described in the protocol)
- Summary of toxicities separated by cohorts with the number of dose-limiting toxicities indicated
- Abstract submissions/publications
- Summary of any recent literature that may affect the safety or ethics of the study

The study principal investigator and Research Patient Coordinator will monitor for serious toxicities on an ongoing basis. Once the principal investigator or Research Patient Coordinator becomes aware of an adverse event, the AE will be reported to the HRPO and QASMC according to institutional guidelines.

12 DATA SUBMISSION SCHEDULE

Case report forms with appropriate source documentation will be completed according to the schedule listed in this section.

Case Report Form	Submission Schedule
On-Study Form	Prior to start of study treatment
Treatment Form Medical History Form	At the end of each cycle

Correlatives Form	Baseline Cycle 3 pre-treatment 6 mos post-C1D1 9 mos post-C1D1 1 yr post-C1D1 15 mos post-C1D1 18 mos post-C1D1 21 mos post-C1D1 Evidence of B-cell reconstitution 2 yrs post-C1D1 3 yrs post-C1D1 4 yrs post-C1D1 5 yrs post-C1D1
Treatment Summary Form	End of treatment
Acute GvHD Form	Baseline Cycle 3 Cycle 4 Cycle 5 Cycle 6 Cycle 7 6 mo f/u
Chronic GvHD Form	Cycle 3 Cycle 4 Cycle 5 Cycle 6 Cycle 7 6 mo f/u 9 mo f/u 12 mo f/u 15 mo f/u 18 mo f/u 21 mo f/u 24 mo f/u
Follow-Up Form	6 mos 9 mos 12 mos 15 mos 18 mos 21 mos 24 mos
Adverse Event Form Immunosuppressive Meds Form	Continuous
Progression Form	Time of progression
Death Form	Time of death

12.1 Adverse Event Collection in the Case Report Forms

All adverse events that occur beginning with start of treatment (minus exceptions defined in Section 7.0) must be captured in the Toxicity Form. Baseline AEs should be captured on the Medical History Form.

Participant death due to disease progression should be reported on the Toxicity Form as grade 5 disease progression. If death is due to an AE (e.g. cardiac disorders: cardiac arrest), report as a grade 5 event under that AE. Participant death must also be recorded on the Death Form.

13 STATISTICAL ANALYSIS

This trial is designed to allow preliminary assessments of safety/tolerability and efficacy of belimumab in the post-allogeneic stem cell transplant setting. No pre-specified hypothesis testing will be performed. All analyses of demographics, biological activity, and safety will be descriptive. A 90% exact binomial confidence interval will be constructed for preliminary efficacy information. Data obtained from correlative studies will be used to identify parameters associated with efficacy from belimumab treatment that will guide design of subsequent larger clinical trials. Age-, disease-, and donor-matched subjects will be used as an institutional control. These control subjects will be identified within the Bone Marrow Transplant and Lymphoma Tissue Bank (HRPO# 201103349). Presently, there are roughly 100 subjects with banked specimens and associated clinical outcomes data that will serve as the comparator in this study in assessing preliminary efficacy. The data from this study will be used for sample size calculation estimates of an expansion cohort in a subsequent phase II study. A total of N=10 patients will be enrolled for this study. Though the sample size was not determined based on statistical power, this would provide us reasonable precision on both safety and feasibility. Based on intensive simulation studies regarding the sample size for pilot and translational studies, Piantadosi (2005) recommends that a sample size of 10 to 20 patients be adequate to provide preliminary information. For safety assessment, for example, there would be 90% chance of observing at least 1 serious adverse event if the true rate is at least 20%. Conversely, there would be less than 10% chance that we would observe 2 or more serious adverse events if the true rate is less than 5%.

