1.1 Graft-versus-Host Disease

Chronic graft-versus-host disease (GvHD) is the most common cause of late morbidity and non-relapse mortality following alloHCT, occurring in roughly 40-60% of long-term survivors [1-3]. Risk factors for developing chronic GvHD include older patient age, use of peripheral blood stem cells versus bone marrow, and lack of T-cell depletion [4, 5]. Chronic GvHD is a multisystem, debilitating, immune-mediated disorder characterized by immunosuppression and immune dysregulation, resulting in increased risk of infections, impaired organ function and reduced quality of life (QOL). Importantly, the incidence of GvHD is on the rise due to multiple factors, including more transplantation of older adults, increased use of mobilized peripheral blood as a stem cell source, increased use of alternative donors (i.e., unrelated or haploidentical donors), and improved early post-transplant survival. Symptoms of chronic GvHD occur gradually, starting on average at 6 months after transplantation. Chronic GvHD targets skin, mouth, eyes, gut, liver, lungs, joints, and genitourinary system; it may be restricted to a single site, but more frequently several organ-sites are included.

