3 PATIENT SELECTION AND ENROLLMENT

3.1 Inclusion Criteria

1. At least 18 years of age
2. ECOG performance status ≤ 2
3. Diagnosis of hematologic malignancy (i.e. acute myeloid leukemia, acute lymphoblastic leukemia, chronic lymphocytic leukemia, chronic myelogenous leukemia, Hodgkin's lymphoma, non-Hodgkin's lymphoma, myelodysplastic syndrome, chronic myelomonocytic leukemia)
4. Use of myeloablative or non-myeloablative conditioning regimen
5. Use of mobilized peripheral blood stem cells from fully HLA-matched related or unrelated donor as a graft source
6. Acute GvHD prophylaxis with methotrexate and tacrolimus
7. Documented complete remission and full donor engraftment (by STR identity testing) on Day +30 bone marrow biopsy
 - a. Complete remission: less than 5% blasts in an aspirate bone marrow sample with a count of at least 200 nucleated cells, no blasts with Auer rods or persistence of extramedullary disease PLUS absolute neutrophil count (ANC) $> 1,500/\mu\text{L}$, platelet count $\geq 50,000/\mu\text{L}$ and no leukemic blasts in the peripheral blood.
 - b. Negative minimal residual disease
 - c. Full donor engraftment by STR testing (either by bone marrow or peripheral blood testing)
8. Adequate end organ function:
 - a. Serum bilirubin $\leq 1.5 \times \text{ULN}$
 - b. Alanine aminotransferase (ALT) and aspartate aminotransferase (AST) $\leq 2.5 \times \text{ULN}$
 - c. Creatinine clearance $\geq 40 \text{ mL/min/1.73 m}^2$ by the Cockcroft-Gault formula
9. Women of childbearing potential must agree to use adequate contraception (hormonal or barrier method of birth control, abstinence) prior to study entry, for the duration of study participation, and for 16 weeks after the last dose of study drug. Should a woman become pregnant or suspect she is pregnant while participating in this study, she must inform her treating physician immediately.
10. Able to understand and willing to sign an IRB-approved written informed consent.

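### The tissue-bank controls are not selected or timed like the trial subjects, so the efficacy comparison carries selection and immortal-time bias whose direction the plan leaves open

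*Combined protocol and SAP*

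**What the plan says.** **Controls.** Section 13 (Statistical Analysis) defines them in one sentence: "Age-, disease-, and donor-matched subjects will be used as an institutional control". It describes the pool as "roughly 100 subjects with banked specimens and associated clinical outcomes data that will serve as the comparator in this study in assessing preliminary efficacy". Section 8.3 (Exploratory Endpoints/Correlative Studies) gives a longer list: "Age- and disease-matched controls with matched conditioning regimens and donor source/mismatch status will be obtained from the Bone Marrow Transplant Tissue Bank". On sampling, Section 8.3 says "These patients have had peripheral blood samples stored at time of transplant, 30 days post-transplant, 100 days post-transplant, 180 days post-transplant, and 360 days" after transplant. Neither section states a clinical eligibility rule, a landmark or an index date for controls.

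**Trial subjects.** Section 3.1 requires "Documented complete remission and full donor engraftment (by STR identity testing) on Day +30 bone marrow biopsy", with negative minimal residual disease as a sub-item. It also requires a fully HLA-matched mobilized peripheral blood stem cell (PBSC) graft and methotrexate/tacrolimus prophylaxis. Section 3.2 excludes chronic GvHD and active grade III-IV acute GvHD at enrollment. Section 5 has treatment start between Day +30 and Day +80. Section 8.2 counts a subject for the secondary endpoints only after at least two cycles, and measures overall survival and relapse from the start of belimumab, although both endpoints are titled by months after transplant.

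**Analysis.** Section 13 plans no hypothesis test, a 90% exact binomial interval for preliminary efficacy, and N=10.

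**The concern.** A subject enters the treated group only after surviving to Day +30 to +80 in a favourable state. A control chosen by the stated matching rule need only resemble that subject in age, disease and donor, and perhaps conditioning. Nothing stops a control from having died, relapsed or developed severe GvHD before the day on which the matched subject started belimumab. Those events could be counted in controls but could never occur in the treated group.

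The protocol's own prognostic factors are also loosely held. Section 1.1 names "use of peripheral blood stem cells versus bone marrow, and lack of T-cell depletion" among the risk factors for chronic GvHD. GvHD prophylaxis appears in neither matching list, and it is unclear whether the donor-source wording in Section 8.3 covers graft source.

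This contrast is the plan's stated means of judging preliminary efficacy. If the groups differ by construction, a difference between them cannot be read as a signal, and at N=10 it cannot be repaired afterwards by adjustment.

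**Working it through.** **The plan's own figures.** Section 13 gives none for the control comparison. Its two safety figures for N=10 reproduce: 1 - 0.8^10 = 0.893 (stated as 90%), and the chance of two or more events at a 5% rate is 0.086 (stated as under 10%). They do not bear on this point.

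**Entry conditions side by side**

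| Condition | Trial subject | Control |
|---|---|---|
| Alive at Day +30 to +80 | Required (Section 5) | Not stated |
| Day +30 MRD-negative remission, full donor engraftment | Required (3.1) | Not stated |
| No chronic GvHD, no active grade III-IV acute GvHD | Required (3.2) | Not stated |
| Fully matched PBSC graft | Required (3.1) | Unclear (donor source/mismatch status, 8.3 only) |
| Methotrexate/tacrolimus | Required (3.1) | Not stated |
| Conditioning | Myeloablative or non-myeloablative (3.1) | Matched in 8.3, absent from 13 |
| Alive to receive Cycle 2, about 2 weeks after Cycle 1 | Required for efficacy (8.2) | No counterpart |
| Clock start for survival and relapse | Belimumab initiation (8.2) | No such date |

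**Clock mismatch.** Twelve months from Cycle 1 Day 1 (C1D1) falls between Day 365 + 30 = 395 and Day 365 + 80 = 445 after transplant. Twelve months from transplant is Day 365.

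**Survival, reading A: controls need not have later samples.** Assume no drug effect. Let S be 12-month survival from transplant in unselected controls and d the share dead before the landmark. Both are assumed: S = 65-75%, d = 5-15%. Survival given alive at the landmark is S/(1 - d):

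- 0.65/0.95 = 0.684, a shift of 3.4 points
- 0.65/0.85 = 0.765, a shift of 11.5 points
- 0.75/0.95 = 0.789, a shift of 3.9 points
- 0.75/0.85 = 0.882, a shift of 13.2 points

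So about 3-13 points in favour of belimumab from early deaths alone, with both groups timed from transplant for simplicity.

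**Survival, reading B: every control has samples to Day 360.** Control survival to Day 360 is then 100% by construction. Against the same landmark values of 68.4-88.2%, the shift is 100 - 88.2 = 11.8 to 100 - 68.4 = 31.6 points, now against belimumab.

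**Chronic GvHD under reading A.** Take the 40-60% in Section 1.1 as the rate g among landmark survivors (an assumption; the protocol gives it for long-term survivors).

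- Leaving early deaths in the control denominator lowers crude control incidence by g × d: from 0.40 × 0.05 = 2 points to 0.60 × 0.15 = 9 points. This works against belimumab.
- Counting controls whose chronic GvHD began before the landmark (assumed share e = 2-10%) raises control incidence by e × (1 - g): from 0.02 × 0.40 = 0.8 points to 0.10 × 0.60 = 6 points. This works in its favour.

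**Scale.** At 5 of 10, the 90% exact interval is 22.2% to 77.8%.

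**The case against.** The best defence is that this is a descriptive pilot of ten subjects. The primary endpoint is safety and does not use the controls, no test is planned, and the only named efficacy statistic is an exact binomial interval that is not described as a between-group contrast. Random error at N=10 is larger than most of the illustrative bias. All of this stands and limits the severity. It does not remove the point: Section 13 still names the bank as the efficacy comparator, and a wide interval does not make the groups comparable.

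A reader might go further than the documents allow in five ways.

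- **That the bias favours belimumab.** This holds for survival and relapse only if controls need no later samples. Read literally, Section 8.3 says the controls have samples to Day 360, which turns the survival bias round.
- **That trial subjects enter event-free.** Sections 3.2 and 5 allow resolved acute GvHD, current acute GvHD of grade II or less, and continuing steroids. The remission and engraftment criterion is set at Day +30, not at C1D1.
- **That graft source is plainly unmatched.** The donor-source wording in Section 8.3 may cover it.
- **That the bank holds marrow or T-cell-depleted transplants.** Section 1.1 lists general risk factors; nothing describes the bank's contents.
- **That phase II will be sized on this contrast.** Section 13 ties sizing to the data from this study, without saying that the difference from controls is the input.

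**Conclusion.** The point holds as a comparability defect in a secondary, descriptive analysis. No section gives controls the trial's eligibility, a landmark or a time origin, and the two matching lists disagree. The contrast therefore carries selection and immortal-time bias.

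Its direction is not fixed. Without a sampling requirement, early control deaths and relapses favour belimumab on survival and relapse. If every control must have reached Day 360, the survival bias runs the other way. Crude chronic GvHD incidence can move either way.

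Every size given is illustrative, because the documents report no early-death, early-relapse or survival rates. The 3-13 points apply only to reading A with 5-15% early deaths and 65-75% 12-month survival. The change should be made because it is cheap and the comparison is otherwise uninterpretable. It does not threaten the primary safety objective.

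**What to change.** Amend Sections 8.3 and 13 together:

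1. Use one matching list in both: age, disease, conditioning and donor type.
2. Restrict controls to those with a fully matched PBSC graft and methotrexate/tacrolimus who met the Day +30 remission and engraftment criterion. Apply MRD status where it is recorded; Section 8.3 does not list it among the available data.
3. Set a landmark at the matched subject's C1D1 day after transplant. The control must then be alive, without relapse, without chronic GvHD and without active grade III-IV acute GvHD.
4. Start the clock at that landmark in both groups, and bring the endpoint titles in Section 8.2 into line with it.
5. Include every treated subject in this comparison, or move the landmark to Cycle 2 in both groups, so that the two-cycle rule adds no guaranteed survival.
6. Do not require Day 180 or Day 360 samples for the clinical-outcome comparison. State what the sampling sentence in Section 8.3 means.
7. Reconcile the two Cycle 1 windows in Section 5.2 (Day +30 to +80 and Day +30 to +60), since the landmark depends on them.

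The cost is a few paragraphs and a database query; Section 8.3 says survival, recurrence, engraftment, GvHD and medication data are already held. Fewer than the roughly 100 banked subjects will qualify, and the documents do not allow that number to be estimated, so it should be counted before outcomes are compared. Section 3 also screens on performance status, organ function and infection. Where the bank lacks these, the remaining imbalance should be reported as a limitation.
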